## **8. SAFETY EVALUATIONS**

All participants will receive a phone call within 1 week after enrollment, and also at Month 1 and Month 2 to follow-up whether they are taking the investigational pills (vitamin C or placebo) daily and whether they have any adverse events from taking the investigational pills (see checklist in Appendix). If any adverse events were found/reported, we will follow them per recommendations of the medical monitor until the event resolves. [name], a nurse practitioner with specialty in heart failure management at UNC Meadowmont Cardiology clinic will serve as a medical monitor on this study. Any adverse event will be reported to [name] in 72 hours or less. [name] will determine the severity of the adverse events and advise whether the participant needs to stop taking the investigational pills, withdraw from the study, or any medical treatment is needed. We will follow [name]' advice immediately.

When subjects have AE (define as new signs and symptoms after taking investigational drugs, such as digestive distress--diarrhea, nausea, abdominal bloating and any other unanticipated adverse events that could possibly be related to the intervention). We will report to

[name] to determine the severity of the AEs (see below). When mild AE is determined, subjects will continue to take their investigational drugs without further treatment and the RA will keep following up subject's AE until AE resolves. When moderate AE is determined, we will ask subjects to stop taking their investigational drug, advise them to seek medical treatment, and continue to follow up until the AE resolves. If severity of any AE is more than moderate, we will ask subjects to seek for emergent medical treatment.

- Mild Adverse Event – Event results in mild or transient discomfort, not requiring intervention or treatment; does not limit or interfere with daily activities (e.g., insomnia, mild headache).
- Moderate Adverse Event – Event is sufficiently discomforting so as to limit or interfere with daily activities; may require interventional treatment (e.g., fever requiring antipyretic medication).
- Severe and undesirable Adverse Event – Event results in significant symptoms that prevents normal daily activities; may require hospitalization or invasive intervention (e.g., anemia resulting in blood transfusion).

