The adverse event information will be reviewed in our monthly team meeting to monitor subject safety. The PI will also monitor the rate of AEs occurring in this study and decide if it is reasonable in light of the rate of AEs in the current literature to continue the study with the medical monitor's input.

The research assistant is responsible to report any AE related to the study to [name] and the PI. The PI will work with the medical monitor to evaluate the event and make a determination of relatedness if the event is related to the study, as it occurs and for notifying the Associate Dean for Research of the UNC School of Nursing and UNC IRB of the occurrence of any adverse event. A scale on relatedness ranging from "Not related to" to "Definitely related to" (Not related to, probably not related to, possibly related to, definitely related to) will be used to evaluate relatedness. Any "definitely related" and "possibly related" events will be reported to the UNC IRB.

The PI will report to the UNC IRB any adverse events that are (1) unexpected, (2) related or possibly related to participation in the research, and (3) serious or suggest that there are new or increased risk(s) to subjects.

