The secondary endpoints are symptom burden, HRQOL, cardiac function, and oxidative stress. For Aim 2 to test the effect of a vitamin C supplementation intervention on the secondary endpoint of HF symptom burden from baseline to 3-month follow-up among 3 groups, we will use repeated measure of ANOVA to detect differences in symptom burden from baseline to 3-month follow-up in the intervention group and compared to the control group from baseline to 3-month follow-up. Similarly, to test the effect of a vitamin C supplementation intervention on the secondary endpoint of HRQOL (cardiac function, and oxidative stress) compared to the control group, we will use repeated measure of ANOVA to detect differences in HRQOL (cardiac function, and oxidative stress) from baseline to 3-month follow-up in the intervention group and compared to the control group from baseline to 3-month follow-up.

Similar analysis will be done for adverse events. to test the effect of a vitamin C supplementation intervention on the frequencies of adverse events compared to the control group, we will use ANOVA to compare frequencies of adverse events during the 3-month period among 3 groups.

Sample Size and Power: The total sample size of 42 participants will be selected as a pilot feasibility study. With 42 patients (14 in each group) and an alpha level of .05, the power of the ANOVA F test to detect a significant group difference will be 80% if the effect size is 0.5.

Interim/safety Analysis. We plan to conduct the interim/safety analysis when we have 50% of the intervention sample, and the findings (as well as adverse events) will be reported to the medical monitor. The medical monitor will make decisions about the safety of continuing (or stopping) the protocol, providing recommendations for recruitment, retention, safety, and other issues as appropriate.

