**10. APPENDIX:**

**Checklist of adverse events for taking high dose of vitamin C supplement**

**Study #:** \_\_\_\_\_ **Data collector:** \_\_\_\_\_

**Date of follow-up:** \_\_\_\_\_ (for Week 1, Month1, Month2, Month3)

1. Diarrhea Yes No
2. Nausea Yes No
3. Abdominal bloating Yes No
4. Others: any other unanticipated adverse events/problems that occurred Yes No  
\_\_\_\_\_ (described what it is)

If any yes for item 1-4, describe in the box: 1) when did the event start, 2) how long did it last, 3) did the participant take any treatment/action, and 4) is it now resolved?

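### Events beyond new signs and symptoms are partly screened for relatedness and expectedness before relatedness is graded, so worsening heart failure, hospitalisation or death can drop out of the three-arm safety comparison

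*Combined protocol and SAP*

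**What the plan says.** The definition in Section 8 (Safety Evaluations) has two parts. The first depends on timing only: "define as new signs and symptoms after taking investigational drugs, such as digestive distress--diarrhea, nausea, abdominal bloating". The second adds "any other unanticipated adverse events that could possibly be related to the intervention", which carries two conditions, unanticipated and possibly related.

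Other wording bears on what is collected:

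- **Calls.** Sections 5 and 8 have staff ask, within a week and at Months 1 and 2, about adverse events that come from the pills.
- **Checklist (Section 10, Appendix).** Diarrhoea, nausea and bloating are asked of everyone as yes/no items. The single open item covers "any other unanticipated adverse events/problems that occurred".
- **Reporting duty.** One sentence in Section 8 sends every adverse event to the medical monitor within 72 hours. A later one says "The research assistant is responsible to report any AE related to the study".
- **Relatedness.** The investigator and monitor then grade each event on four levels: "Not related to, probably not related to, possibly related to, definitely related to".
- **IRB reporting.** Section 8 has three statements. The first is notification to the "UNC IRB of the occurrence of any adverse event". The second covers events graded possibly or definitely related. The third covers events that are "1) unexpected, (2) related or possibly related to participation in the research, and (3) serious", where the last condition is also met by an event that points to new or greater risk.
- **Analysis (Section 9).** "we will use ANOVA to compare frequencies of adverse events during the 3-month period among 3 groups". No separate definition of the counted events is given.

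The documents define no serious adverse event and plan no listing of deaths or all-cause hospitalisations by arm. In the adverse event rules, hospitalisation appears only in the description of the severe grade, which applies once an event already counts.

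**The concern.** A between-arm safety comparison is most useful when events are collected without regard to cause and attribution is judged afterwards. Here part of the attribution is made at collection, by the participant answering a causally worded question or by the research assistant deciding what to pass on.

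The events most exposed are the ones that matter most in this population. Worsening of an existing symptom is not plainly new, and a heart failure admission is hard to call unanticipated when Section 1 describes patients as still symptomatic on optimised treatment and often readmitted.

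Three uses depend on the count: the three-group comparison, the investigator's check of the event rate against the literature, and the monitor's advice on continuing at the interim safety review. A count thinned by opinion on cause suits none of them. If the person screening also knows the allocation, the thinning can differ by arm.

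**Working it through.** **The plan's own figure.** No adverse event figure is stated. The only power statement (80%, 42 participants, effect size 0.5) concerns the ANOVA F test. It reproduces as 80.3% with Cohen's f = 0.5 (degrees of freedom 2 and 39, noncentrality 42 × 0.5² = 10.5). It has no bearing on this point.

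**Step 1. Run typical events through the wording.**

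| Event | Timing part of definition | Second part of definition | Checklist |
|---|---|---|---|
| New diarrhoea, nausea, bloating | Yes | Not needed | Items 1-3, asked of all |
| New headache | Yes | Not needed | Item 4, if unanticipated |
| Worsening of an existing symptom | No, read strictly (not new) | Only if unanticipated and possibly related | Item 4, if unanticipated |
| Heart failure hospitalisation | Only through a new sign or symptom | Only if unanticipated and possibly related | Item 4, if unanticipated |
| Death | Not clearly | Only if unanticipated and possibly related | Item 4, if unanticipated; no participant to answer |

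The last three rows have no certain route into the record. The causal wording of the calls and of the assistant's duty narrows the route further.

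**Step 2. Weight of one omitted participant.** 1/14 = 7.1 percentage points of an arm's proportion.

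**Step 3. How many participants could be affected.** The documents give no three-month hospitalisation risk for this population. Section 1 cites 50% readmission within 6 months of discharge; at constant hazard that is 1 − 0.5^(3/6) = 29.3% at 3 months. Enrolled patients must be more than a month past any admission and not in NYHA class IV, so I use 29.3% only as a high-end reference. The other risks are assumptions.

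| Three-month risk | Expected of 42 (42 × risk) | Chance of at least one, 1 − (1 − risk)^42 |
|---|---|---|
| 5% | 2.1 | 88% |
| 10% | 4.2 | 99% |
| 20% | 8.4 | >99.9% |
| 29.3% | 12.3 | >99.9% |

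The middle rows give the 4 to 8 participants. These are participants with an event that could be omitted; all would be lost only if every hospitalisation were screened out.

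**Step 4. Same screening in all arms (illustration).** Assume true event risks of 20% on placebo (n = 14) and 50% on vitamin C (both arms pooled, n = 28), compared by Fisher's exact test at 0.05. Power is 45% with full recording, 12% if half of events are recorded and 1% if a quarter are.

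**Step 5. Screening that differs by arm (illustration).** Assume an equal true risk of 29.3%, with half of events recorded on vitamin C and a tenth on placebo. Recorded risks are 0.293 × 0.5 = 14.6% and 0.293 × 0.1 = 2.9%, a difference produced by recording alone.

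**Step 6. IRB statements.** An expected, possibly related, non-serious event that suggests no new risk is reportable under the first two statements but does not meet the third. An event graded probably not related is reportable under the first only.

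**The case against.** Much of the collection is not screened for cause. The first part of the definition rests on timing, the digestive items are asked of everyone, and the checklist's open item has no relatedness condition. Section 8 also sends every adverse event to the monitor, and its severity examples (insomnia, fever, anaemia) suggest that more than tablet side effects was intended. A hospitalised patient will often have a new sign or symptom and so qualify under the first part. All of this stands, and it limits the point to a partial screen in inconsistent text.

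It does not close the gap. The open item still requires the event to be unanticipated, and the instruction covering every adverse event takes its meaning from the definition. The promise to pass new signs or symptoms to the patient's health care team does not put them in the safety analysis.

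Stronger readings that a reader might infer, and that the documents do not support:

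- *Every adverse event is filtered by opinion on cause.* The timing-based part and the digestive items contradict this.
- *The lowest relatedness grade can never occur.* An event that qualifies on timing can be graded not related, and so can one that looked possibly related at first.
- *The definition, not the checklist, decides what is analysed.* Section 9 does not name its source; the checklist is the only collection form shown.
- *The comparison is biased between arms.* That needs the screener to know the arm. Section 3 says single blind without saying who is blinded.
- *The narrowest IRB statement overrides the others.* None of the three is worded as exclusive, so following the broadest satisfies all.

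**Conclusion.** The point holds as a defect in collection wording that can remove relevant events from the safety comparison and the monitor's review. It concerns events outside the three digestive items, chiefly worsening heart failure, hospitalisation and death.

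Under-counting follows from the wording if it is applied as written. Bias between arms is conditional on the screener knowing the allocation, which the documents neither establish nor exclude. The 7.1 points per omitted participant is arithmetic. The 4 to 8 of 42 rests on an assumed 10-20% risk and on total omission, so it should not be read as the number that will be missed. With 14 per arm the comparison is weak even with complete recording; the stronger reason to change the wording is that the monitor needs the full set of events.

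The three IRB statements need no assumption: they set different thresholds and should be one.

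**What to change.** For recording and analysis:

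1. Count any new or worsening sign, symptom or medical event after the first tablet, including all-cause hospitalisation and death, whether or not it is thought related or expected.
2. Remove the limits to *unanticipated*, possibly related, pill-caused and study-related events from the definition, the call wording, the research assistant's duty and the checklist.
3. Grade relatedness afterwards, by assessors masked to arm.
4. State in Section 9 which record feeds the comparison, that it uses all recorded events, and that the related subset comes second.
5. Reconcile the three IRB reporting statements into one.

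One consequence must be handled with it. Section 8 attaches treatment actions to the severity grades without a relatedness condition, so a wider definition would also widen the reach of those actions, with possible effects on exposure and the primary endpoint. The sponsor must reconcile the action rules with the wider recording definition; no clinical rule is proposed here.

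Cost: wording changes to the protocol and checklist, and more events to log and review. The calls are already planned, so this is a cheap improvement.

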### 3. INVESTIGATIONAL PLAN

**Design.** This project is a feasibility pilot study to test the effects of vitamin C supplementation, and to obtain initial estimates of effect size to support a future RCT. The proposed vitamin C supplementation intervention study is a three-group, single blind, placebo controlled prospective design (control n=14, Vit C 500mg n=14, Vit C 1000mg n=14). The most commonly tested dose of vitamin C in current trials on vitamin C supplementation is 1 g/day. The primary endpoint to evaluate the effect of vitamin C supplementation is serum vitamin C level. The secondary outcomes include HF symptom burden, HRQOL, cardiac function, and oxidative stress. The variables would be measured in person at baseline and at 3 months include: HF symptom burden, HRQOL, PROMIS fatigue, depression and sleep disturbance, serum vitamin C level, biomarker of cardiac function (i.e., cardiac output using impedance cardiograph) and oxidative stress (8-iso-PGF2a isoprostane, see below in detail), as well as demographic, clinical, and other variables that can affect study outcomes (e.g., age, gender, race/ethnicity, body mass index, serum creatinine) and medications. HF symptom burden and HRQOL will also be measured at Month 1 and 2 by phone. We will also collect data to assess feasibility (recruitment, retention, attrition rates).

**Sample and Setting.** A total of 42 participants (14 per group) will be randomly assigned to either the control or the intervention group. Patients with HF will be recruited at the University of North Carolina Hospital internal medicine/cardiology outpatient clinics.

**Inclusion/Exclusion Criteria.** Inclusion criteria include patients (a) have a diagnosis of chronic HF. The diagnosis and etiology of chronic HF will be confirmed by a HF cardiologist using established criteria, (b) have undergone evaluation of HF and optimization of medical therapy, (c) are not taking any vitamin C supplementation at all or are willing to stop taking their current vitamin C supplementation, (d) able to read and speak English, (e) have >1 month from any inpatient hospitalization, (e) treating cardiology healthcare provider indicates the individual is a good candidate for this study that involves 3 months of vitamin C supplement of 500 mg/day, 1g/day, or placebo, (f) Per treating healthcare provider's assessment, patient's projected lifespan is greater than or equal to 6 months.

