Exclusion criteria include: (a) stage D HF or New York Heart Association (NYHA) functional class IV, (b) history of renal stones or renal disease (serum creatinine >1.5), (c) history of glucose-6-phosphate dehydrogenase deficiency (G6PD) and (d) cognitive impairment that precludes giving informed consent or ability to follow protocol instructions, (e) originally taking vitamin C 500mg/day or more, (f) women who are pregnant.

Female patients with HF are considered past child-bearing potential: 1) if they are ≥60yrs of age or 2) if they are age 50 to 59 years and have not menstruated for 12 months (will confirm by self-report). For women < 50 years old (with child-bearing potential), we will confirm by self-report that they are not pregnant and confirm this by completing a urine pregnancy test prior to enrollment and assess for likelihood of pregnancy on a monthly basis.

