## **5. PROCEDURES AND RECRUITMENT STRATEGY**

Permission for this study will be obtained from the University of North Carolina at Chapel Hill Institutional Review Board. A dedicated and trained research assistant will recruit HF patients from the UNCH clinics. A list of HF patients who will come to the UNCH clinics will be generated and obtained from the staff in charge for the scheduling information in the clinics one week before patients' visits. On the day that the potential participants come to the clinic, the research assistant will screen the potential participant's eligibility based on inclusion and exclusion criteria. The research assistant also will consult with the potential participant's treating healthcare provider to make sure the potential participant is appropriate for the study and patient's projected lifespan is greater than or equal to 6 months. Once the research assistant confirms the potential participants are eligible and gets approval from the provider, the research assistant will approach and briefly explain the study to recruit potential participants while they wait to see their physicians. If potential participants are interested in participation, the research assistant will then confirm eligibility. For eligible patients, study requirements will be explained in detail. If the patient agrees to participate, a signed informed consent will be obtained based on consent process (see below) and we will administer the survey, measure cardiac impedance and obtain the blood samples. All eligible patients will be randomized to either the control group or to the intervention group using the Medsharing application for clinical trials.

**Baseline visit.** Data on socio-demographics, clinical characteristics medications, symptom burden, PROMIS depression, fatigue, and sleep disturbance, HRQOL, will be collected at the beginning of the visit and blood will be drawn to measure serum vitamin C level and oxidative stress (8-iso-PGF2a isoprostane). All participants will be asked to return their respective supplementation bottles to the research assistant at Month 3. We will count pills to determine patient adherence to taking the placebo or vitamin C supplementation.

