**Patient Safety and Confidentiality.** All private health information (PHI) will be kept strictly confidential and subject to the Health Insurance Portability and Accountability Act (HIPAA). All study data in transit will be stored on an encrypted lap top computer stored and locked within the office of the study PI. All transit study data will be back up to the secure SON server that is password protected and maintained by information technology support and then be deleted from the encrypted laptop computer within 72 hours after data are collected. The secure SON server can only be accessed by study personnel on this study. Any new signs or symptoms reported by the patient to the research team will be promptly communicated to the patient's health care team. At the baseline visit, patients will be assessed for any vitamin supplementation, serum creatinine and history of kidney stones. If subjects are currently taking a vit C supplement, we will advise them to stop taking any vitamin C supplement while they are on the study. We also will carefully review with the subjects if they are taking any multivitamin that contains vitamin C and advise them to stop taking any multivitamin that contains vitamin C. Although vitamin C is a water-soluble vitamin, we have implemented these steps to insure safety before randomization.

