## 9. DATA MANAGEMENT AND STATISTICAL ANALYSIS

Each participant will be assigned an anonymous ID. Data will be collected using touchscreen laptop computer, and the REDCap (Research Electronic Data Capture) system, a secure web-based application that is designed to support data capture for research studies.

All data analyses will be performed using SPSS 24.0. All estimates will be obtained along with 95% confidence intervals.

Descriptive statistics: All data with approximately symmetric distributions will be described by their mean and standard deviation, as well as number/frequency and percentage (for Aim 3) and variables with skew will be described by the median and interquartile range. Categorical variables will be shown as total number and proportion and will include: race, sex, NYHA functional class, and comorbidity. Associations between categorical variables will be tested by the Chi Square test ( $X^2$ ) or McNemar's test. Continuous variables will include symptom burden, PROMIS depression, fatigue, and sleep disturbance, HRQOL, cardiac function, serum vitamin C levels and biomarker for oxidative stress. Associations between categorical and continuous variables will be tested by t-test and analysis of variance (ANOVA). Associations between continuous variables will be tested using Pearson's correlation coefficient ( $r$ ) will be used to establish if the correlation coefficient is statistically different.

Efficacy analysis for the specific aims is described below:

The primary endpoint is serum vitamin C level. For Aim 1 to test the effect of a vitamin C supplementation intervention on the primary outcome (serum vitamin C level) from baseline to 3-month follow-up among 3 groups, we will use repeated measure of ANOVA to detect differences in the serum vitamin C level from baseline to 3-month follow-up in the intervention group and compared to the control group from baseline to 3-month follow-up.

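### Prior vitamin C users give their baseline blood at the visit where they are told to stop: the between-arm contrast stays unbiased, but within-arm change is lowered and the change-based test loses precision

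*Combined protocol and SAP*

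**What the plan says.** Section 3 admits patients who "are not taking any vitamin C supplementation at all or are willing to stop taking their current vitamin C supplementation", and excludes those "originally taking vitamin C 500mg/day or more". Lower-dose users are therefore eligible.

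Section 8 fixes the timing: "At the baseline visit, patients will be assessed for any vitamin supplementation". Of current users it says "we will advise them to stop taking any vitamin C supplement while they are on the study", and for multivitamins the team will "advise them to stop taking any multivitamin that contains vitamin C". It places these steps before randomisation, but does not say they come before the blood draw.

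Section 5 has screening, consent, questionnaires, impedance and blood sampling on one clinic day. At the baseline visit "blood will be drawn to measure serum vitamin C level and oxidative stress (8-iso-PGF2a isoprostane") is the instruction. No washout, second pre-treatment sample, or stratification by prior use is described.

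Section 9 analyses the primary endpoint by repeated-measures ANOVA, to "detect differences in the serum vitamin C level from baseline to 3-month follow-up in the intervention group" and against control. Section 7 collects potential confounders, but no covariate enters any model in Section 9.

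**The concern.** The primary endpoint is the serum level of the substance that some patients are told to stop. In a prior user, change from baseline to Month 3 mixes two things: stopping the old supplement and starting the study pill. A placebo patient who was a user can fall for the first reason alone, and a user on an active arm will appear to respond less.

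Two things are at stake. One is the meaning of any within-arm change reported under Aim 1. The other is the precision of the between-arm test, in a pilot of 14 per arm that is meant to supply effect-size estimates for a later trial.

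**Working it through.** **1. The plan's own figure.** Section 9 gives 42 patients, three arms, alpha 0.05, effect size 0.5 and 80% power. Read as Cohen's f, the noncentrality is 42 × 0.5² = 10.5 on 2 and 39 degrees of freedom, and power is 80.3%. The figure reproduces. Read as a standardised difference between two arms of 14, 0.5 would give 26.2%, so f is the intended metric.

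**2. What is tested.** With two time points, the group-by-time test of a repeated-measures ANOVA is a one-way ANOVA on change scores.

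**3. Model.** Let p be the share of prior users, d their baseline elevation in SD units, and r the baseline to Month 3 correlation. Assume equal SDs at both times without supplementation, and that users have stopped by Month 3. Then:

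- the expected within-arm change shifts by −p·d;
- the variance of change rises from 2(1 − r) to 2(1 − r) + p(1 − p)d²;
- f falls to 0.5 × √[2(1 − r) / (2(1 − r) + p(1 − p)d²)].

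For Month 3 adjusted for baseline alone, the residual variance is 1 − r²/(1 + p(1 − p)d²), and f is 0.5 × √[2(1 − r) / residual variance].

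The documents give none of p, d or r, so the values below are assumptions. f is held at 0.5 on the change scale.

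**4. Results at r = 0.5**, where 2(1 − r) = 1 (noncentral F, 39 error degrees of freedom):

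| p | d | Within-arm shift (SD) | Variance of change | f | Power, change test | Power, Month 3 adjusted for baseline |
|---|---|---|---|---|---|---|
| 0 | – | 0 | 1.00 | 0.500 | 80.3% | 90.7% |
| 0.1 | 0.5 | −0.05 | 1.02 | 0.494 | 79.4% | 90.5% |
| 0.2 | 1.0 | −0.20 | 1.16 | 0.464 | 73.9% | 89.3% |
| 0.3 | 1.0 | −0.30 | 1.21 | 0.455 | 71.9% | 89.0% |
| 0.3 | 1.5 | −0.45 | 1.47 | 0.412 | 62.8% | 87.5% |
| 0.4 | 1.5 | −0.60 | 1.54 | 0.403 | 60.7% | 87.1% |

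Worked row (p = 0.3, d = 1): 0.3 × 0.7 × 1² = 0.21, so the variance is 1.21 and f = 0.5/√1.21 = 0.455.

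In simulation the adjusted model runs slightly lower, about 85–89% with prior users present, because the covariate costs a degree of freedom and baseline differs by chance between arms. Adding prior use as a covariate gives about 88–90%.

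**5. Bias and error rate, by simulation** (40,000 trials per setting, r = 0.5, true changes 0, 1.06 and 1.06 SD). With p = 0.3 and d = 1:

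- mean changes become −0.30, 0.76 and 0.76;
- active minus placebo stays at 1.06;
- its standard error rises from 0.378 to 0.414;
- power falls from 80.5% to 71.8%.

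With no treatment effect, the group-by-time test rejects in 4.9% to 5.2% of trials. A within-placebo test, were one run, would show a false change in 15.6% of trials instead of 5%, and in 37.8% at p = 0.4 and d = 1.5.

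**6. Higher correlation.** At r = 0.7, p = 0.4 and d = 1.5, the change test has 51.3% power. Adjustment for baseline alone gives about 75%, and adding prior use gives about 85%.

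**The case against.** The strongest reply is that the trial is randomised. Prior users fall into each arm by chance, so the between-arm difference has no expected bias and the test keeps its size. That stands, and step 5 confirms it. A reader might infer that the primary comparison is biased or invalid; the design does not support that. Chance imbalance in users between arms is real, but it is already counted in the added variance and is not a further harm.

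Second, Section 9 is ambiguous. Its sentence may describe one model rather than a separate within-arm test, and it names no test within placebo. Section 3 does not say that the effect sizes for a future trial are within-arm changes. The raw between-arm difference is unbiased; only an effect standardised by the SD of change shrinks. This stands, so the within-arm point applies only to whatever within-arm change is reported.

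Third, the size is assumed. Prior intake is capped below 500 mg/day. With 10% users raised by 0.5 SD, the loss is about one point (80.3% to 79.4%), and with no users it is nil. Even with 10% users, an arm of 14 would contain none with probability 0.9¹⁴ = 23%, so lowered change in every arm is a statement about expectation.

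Fourth, much of the power regained has nothing to do with supplements: baseline adjustment gives about 90% at r = 0.5 with no prior users. This stands too. What remains is that the plan, as written, neither adjusts for the baseline it collects nor uses the prior-use assessment it already makes.

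**Conclusion.** The concern holds in a limited form. Prior users can have a supplemented baseline, and Section 9 analyses change from it without adjustment. Within-arm change is lowered in expectation by the share of users times their elevation: 0.05 to 0.60 SD over the assumed ranges. At r = 0.5, power of the change-based test falls from 80% to between about 79% and 60%.

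These figures rest on assumed values for the share of users, their elevation and the correlation, and on f = 0.5 on the change scale. The documents do not show where in the range this trial lies.

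The finding does not extend to bias in the randomised comparison. Nor should the whole gap between about 60% and about 88–90% be put down to prior supplement use, because baseline adjustment helps regardless. At r = 0.5 the prior-use term adds little beyond baseline adjustment; at r = 0.7 it can matter (about 75% to 85% in the most affected setting).

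**What to change.** In Section 9, Aim 1, make the primary estimate the between-arm difference in Month 3 serum vitamin C, adjusted for baseline serum level and for prior vitamin C or multivitamin use (yes/no). State that within-arm changes are descriptive and are not evidence of effect. Add a sensitivity analysis excluding prior users; because prior use is fixed before randomisation, this remains a randomised comparison.

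Section 8 already assesses supplement use, but as a safety step. The answer must be entered in the study dataset as an analysis variable.

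The cost is wording in the analysis section, one data field, and one or two degrees of freedom (39 to 38 or 37). No extra visit, sample or change to patient management is needed. If no users enrol, the prior-use term drops out and the baseline adjustment still earns its place. This is a free improvement to the plan.
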